5.3.2 Study treatment adjustments or interruptions

Study-specific criteria for interruption and discontinuation of study treatment were pre-specified in the protocol section 5.1.12. The protocol did not allow any study treatment dose adjustments.

Study treatment interruptions are assessed via the compliance variables described in Section 5.3.1.2 and the assessment AEs leading to changes in study treatment as described in Section 5.5.5.

Subjects with at least one interruption: Derived as subjects with ‘Study treatment exposure, interruptions excluded’ < ‘Duration of Study Treatment’, based on the definitions in Section 5.3.1.1.

Total duration of interruption(s) (days) is derived as ‘Duration of Study Treatment’ – ‘Study treatment exposure, interruptions excluded’.

5.3.3 DMF exposure and compliance

Exposure and compliance with DMF information will be taken from the Drug Log - DMF (Tecfidera) eCRF (collects information on DMF start date, end date, dose, frequency and reason for treatment end). All DMF dose changes, interruptions and discontinuations are to be reported here.

5.3.3.1 DMF exposure during study treatment

The on-study DMF start date is defined as:

- the study treatment start date (as defined in Section 5.3.1.1) for subjects who were receiving DMF on study treatment start date, as documented in the Drug Log – DMF eCRF;
- the earliest DMF start date documented in the Drug Log – DMF eCRF that is after the study treatment start date, for subjects who were not DMF on study treatment start date, as documented in the Drug Log – DMF eCRF.

The DMF end date is defined as latest DMF end date documented in the Drug Log – DMF eCRF. If the end date of the DMF record with the latest start date is missing, DMF is assumed to be ongoing at study treatment EOT and the DMF end date is imputed with study treatment EOT.

The following exposure variables are derived:

Duration of DMF treatment on study (days) = DMF end date – on-study DMF start date + 1 day. Duration of DMF Treatment on study is also derived in weeks (days divided by 7), months (days divided by 30.4375), and years (days divided by 365.25).

Duration of DMF Treatment on study is categorized as follows: ≤ 24 weeks (168 days), > 24 weeks to ≤ 48 weeks (336 days), > 48 weeks to ≤ 72 weeks (504 days), > 72 weeks to ≤ 96 weeks (672 days), > 96 weeks to ≤ 120 weeks (840 days), > 120 weeks to ≤ 144 weeks (1008 days), > 144 weeks (1008 days).

‘**DMF treatment exposure, interruptions excluded**’ equals the ‘Number of days with DMF intake documented’ between study treatment start date and study drug EOT for a subject overall as defined as part of the compliance derivations described in Section 5.3.3.2

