- **Number of relapses in the year prior to study entry**, as reported in the corresponding question on the ‘MS History - Relapse’ eCRF (i.e., not based on recorded onset dates of previous relapses). Data collected at re-screening overwrites the initially entered data.
- **Number of relapses in the 2 years prior to study entry** as reported in the corresponding question on the ‘MS History - Relapse’ eCRF (i.e., not based on recorded onset dates of previous relapses). Data collected at re-screening overwrites the initially entered data.
- **Prior MS treatment other than DMF (yes/no)** (‘yes’ if any MS treatment recorded on then ‘MS Specific Treatment History’ eCRF form or as prior concomitant medications on the

‘Study-concomitant therapy - Disease-modifying treatment for MS’ eCRF; otherwise ‘no’ if no such medications are recorded).

- **Months on DMF at screening** defined as [Date of screening – DMF start date] in days / 30.4375. DMF start date is defined as the earliest DMF start date documented in the Drug Log – DMF eCRF. In case of partially missing DMF start date, the start date is imputed to the latest possible date, see Section 12.1.1 for full details.
- **Relapses in the previous 6 months prior to study entry while on treatment with DMF (0, 1, ≥ 2)** number of relapses recorded in the 6 months prior to date of screening based on recorded onset dates of previous relapses (‘MS History – Relapse’ eCRF form) and recorded start/end dates of DMF treatment.
- **Presence of T1 Gd+ lesions (yes/no) in the previous 12 months prior to study**, as provided by sites (yes/no) - (‘MS history - MRI’ eCRF form).
- **Presence of T1 Gd+ lesions (yes/no)** on baseline MRI scan as provided by the MRI central reading.
- **Number of documented T1 Gd+ lesions** on baseline MRI scan as provided by the MRI central reading.
- **Presence of new or enlarging T2 (yes/no) in the previous 12 months prior to study**, as provided by sites (yes/no) - (‘MS history - MRI’ eCRF form).
- **Volume of T2 lesions** on baseline MRI scan as provided by the MRI central reading.
- **Smoking status** (Current smoker, Former smoker, Never smoked), taken from ‘Smoking status’ eCRF.

Note: For re-screened subjects, information for baseline characteristics ‘at screening’ is taken from the last Re-screening Visit, if available, instead of the Screening Visit.

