5.3.3.2 Compliance with DMF treatment during study treatment

Compliance is assessed as the percentage of days from the date of first study drug intake until EOT with DMF intake documented in the eCRF:

$$\frac{\text{no. of days with DMF intake documented}}{(\text{date of EOT-study treatment start date}) + 1 \text{ day}} \times 100$$

Note: Compliance below 100% is not necessarily indicative of a deviation from the protocol since the protocol mandates dose interruptions for certain very specific safety scenarios as well as based on investigator's judgment.

For reporting, the calculated compliance is categorized as follows: 100%, 99% – < 100%, 80% – < 99%, 50% – < 80%, > 0% – < 50%, 0%.

The number of days with DMF intake documented is derived as follows:

On the 'Drug Log - DMF' eCRF log form, each record collects 'DMF start date', 'DMF end date', and 'Individual dose'. If, for a record, the 'Individual dose' is > 0, it is assumed that the subject took DMF for each day covered by the record. For each record, the start date is defined to be the maximum of (DMF start date associated with the record, study treatment start date), and the end date is defined to be the minimum of (DMF end date associated with the record, EOT date).

The 'Number of days with DMF intake documented' for a subject overall is derived as the sum across all DMF drug log records.

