12.1.1 Previous / concomitant therapies date imputation

The following imputation of partial dates is made:

Previous therapies: Impute partial start date with lower limit, and partial end date with minimum of upper limit and study treatment start date – 1. Missing dates are not imputed.

Treatment concomitant therapies ongoing at study treatment start: Impute partial start date with lower limit and partial end date with upper limit. Missing dates are not imputed.

Treatment concomitant therapies not ongoing at study treatment start: Impute partial start date with maximum of lower limit and study treatment start date, impute partial end date with upper limit. Missing dates are not imputed.

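### DMF duration in SAP 5.3.3.1 is cut at end of study treatment only when the DMF stop date is missing, so a DMF stop recorded after EOT adds post-treatment days to a descriptive exposure summary

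*SAP*

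**What the plan says.** The heading "5.3.3.1 DMF exposure during study treatment" sets the scope: DMF taken while the subject is on study drug. Within that section there are two rules for the end date.

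- Stop recorded: "The DMF end date is defined as latest DMF end date documented in the Drug Log".
- End date missing on the record with the latest start: "DMF is assumed to be ongoing at study treatment EOT and the DMF end date is imputed with study treatment EOT".

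Duration is then "DMF end date – on-study DMF start date + 1 day". No cap is added. It is converted to weeks, months and years and put into 24-week categories.

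The other variable in the same section, DMF exposure with interruptions excluded, counts days "between study treatment start date and study drug EOT for a subject overall". The compliance derivation in 5.3.3.2 caps each log record explicitly: "the end date is defined to be the minimum of (DMF end date associated with the record, EOT date").

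Section 9.5.2.1 summarizes the 5.3.3.1 exposure by treatment group and adds an overall subject-year total.

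On a separate variable, months on DMF at screening, Section 5.2.2 says that for a partial DMF start date "the start date is imputed to the latest possible date, see Section 12.1.1 for full details". Section 12.1.1 says, for therapies ongoing at study treatment start: "Impute partial start date with lower limit and partial end date with upper limit".

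**The concern.** The two end-date rules use different cut-offs. Take two subjects with the same DMF intake up to EOT. If one later stops DMF and the stop is logged, that subject's duration runs past EOT. If the other never stops, the duration ends at EOT. The subject with the longer real DMF use can receive the shorter duration.

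Reading *on study* differently does not help. If the period is meant to end at EOT, the recorded-stop rule is too long. If it is meant to end at end of study (EOS), the missing-date rule is too short.

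At stake is the accuracy of one descriptive table: DMF duration, its categories and the subject-years built on it. The duration would also disagree with the exposure that excludes interruptions. A reader who subtracts one from the other, as 5.3.2 does for study drug, would take post-treatment days for interruption.

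**Working it through.** The SAP states no DMF exposure figure, so there is nothing to reproduce. The check applies the two derivations to the same hypothetical subjects.

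**Can a DMF stop be recorded after EOT?** Section 5.3.3 has all DMF dose changes, interruptions and discontinuations entered in the DMF log and gives no time limit. Table 3, note 17, foresees that stopping DMF may be considered after a low lymphocyte count at the follow-up visit, about 30 days after the last dose. So the case is foreseeable.

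**Does another section add the cap?** No. Section 12.4 deals with incomplete study-treatment dates and says it is not used for exposure variables. Section 9.5.2.1 only refers back to 5.3.3.1.

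**Per-subject illustration.** Assumed dates: DMF on-study start Day 1, EOT Day 336, DMF taken daily through EOT.

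- 5.3.3.1 as written: duration = recorded end (or EOT if missing) − start + 1.
- With the 5.3.3.2 cap: duration = min(recorded end, EOT) − start + 1.

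| DMF stop | As written | Category as written | With cap | Excess |
|---|---|---|---|---|
| Day 300 (before EOT) | 300 d | >24 to ≤48 wk | 300 d | 0 |
| At EOT | 336 d | >24 to ≤48 wk | 336 d | 0 |
| None recorded (ongoing) | 336 d | >24 to ≤48 wk | 336 d | 0 |
| EOT + 30 | 366 d | >48 to ≤72 wk | 336 d | 30 |
| EOT + 90 | 426 d | >48 to ≤72 wk | 336 d | 90 |
| EOT + 180 | 516 d | >72 to ≤96 wk | 336 d | 180 |

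The excess equals the days from EOT to the recorded stop. It is zero for stops on or before EOT. Exposure with interruptions excluded is 336 days in every row except the first, where it is 300.

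**Aggregate range.** The 136 randomized subjects are from Section 2. Assume 336 days each: 136 × 336 / 365.25 = 125.1 subject-years. The counts and delays below are also assumptions, because the SAP gives none.

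- 5 subjects at EOT + 30: 5 × 30 / 365.25 = 0.41 subject-years, 0.3%.
- 14 subjects at EOT + 90: 14 × 90 / 365.25 = 3.45 subject-years, 2.8%.
- 34 subjects at EOT + 180: 34 × 180 / 365.25 = 16.76 subject-years, 13.4%.

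**Partial DMF start date.** Section 12.1.1 has three rules. Previous therapies, and therapies ongoing at study treatment start, take the lower limit. Therapies not ongoing at treatment start take the later of the lower limit and treatment start. None is the latest-possible-date rule for which 5.2.2 cites it. For a year-only start date in a non-leap year, the two rules differ by 364 / 30.4375 ≈ 12.0 months. For a missing day they differ by at most 30 / 30.4375 ≈ 1.0 month. A year-only date in the screening year, taken at its upper limit, could fall after screening and give negative months on DMF.

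**The case against.** Several limits on the point are fair and stand.

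- **The error is conditional.** It needs a DMF stop recorded after EOT. For subjects who do not enter the post-treatment observation period, EOS is the follow-up visit at 30 days with a 7-day window, so a stop recorded within the study and visit window adds at most about 37 days. A larger excess needs a subject followed in the observation period.
- **Stops during treatment are handled correctly.** The deviation list (PD_PP.132) treats staying on study drug after stopping DMF as an important deviation. A DMF stop during treatment should therefore not normally precede a long further stretch of study drug, and the rule gives the right answer for it in any case.
- **EOT-limited figures are also derived.** Exposure with interruptions excluded and compliance are both cut at EOT. Section 9.5.2.1 does not say which exposure variable is summed to subject-years. Duration is the likely one, because it is the only one derived in years.
- **The start-date point is mainly a bad cross-reference.** Section 5.2.2 states its own DMF rule, and the list of therapy forms in 5.2.3 omits the DMF log, so 12.1.1 arguably does not govern it. The footnote to Table 8 is worded more broadly, which leaves some room for doubt.

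A reader might infer more than the SAP supports:

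- That DMF subject-years *are* overstated. They can be; nothing shows that any subject had such a stop.
- That the distortion is several-fold. With study drug stopped on Day 84 and DMF on Day 420, the ratio is 420 / 84 = 5, but those dates are invented and describe one subject, not the table.
- That safety conclusions are affected. The adverse-event and laboratory incidence summaries in Section 9.9 are counts and percentages of subjects; none uses DMF duration as a denominator.
- That the arms are distorted differently. This would need a difference between arms in post-EOT DMF stops, on which the SAP is silent.

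None of this supplies the missing cap.

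**Conclusion.** The inconsistency in 5.3.3.1 is real, and no other section removes it. Programmed as written, DMF duration is too long for any subject with a DMF stop recorded after EOT, measured against the section's own heading and the EOT-limited variables beside it. The affected outputs are the descriptive DMF duration, its categories and, probably, the subject-years in 9.5.2.1.

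The size is unknown. It is nil if no such stop was recorded, and about 0.3% to 13% of subject-years across the assumed scenarios. Even a 30-day excess can move a subject up one category when EOT falls at a category boundary, as in the illustration.

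Efficacy results, adverse-event percentages, DMF compliance and exposure with interruptions excluded do not change. The partial-start-date mismatch is minor and affects only months on DMF at screening; for subjects already on DMF at study treatment start, on-study duration begins at that date regardless.

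**What to change.** - **Section 5.3.3.1:** define DMF end date = min(latest documented DMF end date, study treatment EOT), and keep EOT when the end date is missing. This matches 5.3.3.2 and costs one line of derivation.
- **Section 9.5.2.1:** name the variable that is summed to subject-years.
- **Section 5.2.2 (minor):** correct the cross-reference to 12.1.1, or add a DMF-specific line there. State one imputation rule for a partial DMF start date, bounded so that the imputed date is not after screening.

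No new data, model or output is needed.

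### The DMF end-date rule in SAP 5.3.3.1 checks neither dose nor start date and is not capped at EOT, so the DMF duration variable can be overstated

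*SAP*

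**What the plan says.** Section 5.3.3 names a single source, the DMF drug log. It holds start date, end date, dose, frequency and reason for treatment end, and "All DMF dose changes, interruptions and discontinuations are to be reported here".

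Section 5.3.3.1 then sets the DMF end date in two steps. The base rule is: "The DMF end date is defined as latest DMF end date documented in the Drug Log – DMF eCRF". The exception concerns an open record: if the end date of "the DMF record with the latest start date is missing, DMF is assumed to be ongoing at study treatment EOT", then "the DMF end date is imputed with study treatment EOT". Neither step mentions dose, the record's start date relative to EOT, or an upper limit at EOT. The result goes directly into *Duration of DMF treatment on study*, which is "DMF end date – on-study DMF start date + 1 day", and into its 24-week categories.

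Section 5.3.3.2 counts intake days from the same log under different conditions. Dose matters: "If, for a record, the 'Individual dose' is > 0, it is assumed that the subject took DMF for each day covered by the record". Each record is also trimmed: its start is moved up to study treatment start if earlier, and "the end date is defined to be the minimum of (DMF end date associated with the record, EOT date". The total feeds DMF compliance and the second exposure variable of 5.3.3.1, which excludes interruptions.

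Sections 9.5.2.1 and 9.5.2.2 summarise DMF exposure, total subject-years and compliance by arm on the safety set.

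**The concern.** Two neighbouring derivations read the same log differently. The intake count asks whether the dose is above zero and stops at EOT; the end date does neither. A dose condition is needed only if a zero-dose record can occur, so the SAP allows for such records in one place and overlooks them in the other.

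The heading of 5.3.3.1 limits the variable to the time on study treatment, yet its end date can come from a record that shows no intake, from a record that begins after study treatment ended, or from a date beyond EOT. DMF use after EOT is foreseeable: footnote 17 to Table 3 discusses DMF at the follow-up visit.

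In an add-on trial, the by-arm description of background therapy tells the reader whether DMF was kept up equally. An overstated duration in one arm would blur that picture. The stake is descriptive.

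**Working it through.** The SAP gives no figure to reproduce. The check applies both rules literally to assumed log records.

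**Assumed inputs.** Study treatment starts on Day 1 and EOT is Day 200. The subject is already on DMF at Day 1, so the on-study DMF start is Day 1. Where a record has no end date, the intake count is taken to use EOT.

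**Formulas.**
- Duration (5.3.3.1) = DMF end date − 1 + 1.
- Intake days (5.3.3.2) = sum over records with dose > 0 of min(record end, 200) − max(record start, 1) + 1.
- Compliance = intake days / 200.
- Restricted duration = the same duration formula, using only records with dose > 0 that start by EOT, with the end date capped at EOT.

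| Log pattern | SAP duration | Restricted duration | SAP intake days | SAP compliance |
|---|---|---|---|---|
| A. DMF to Day 100, record closed, nothing later | 100 | 100 | 100 | 50% |
| B. As A, plus an open zero-dose record from Day 101 | 200 | 100 | 100 | 50% |
| C. As A, plus an open restart from Day 240 | 200 | 100 | 61 | 30.5% |
| D. DMF throughout, record closed on Day 230 | 230 | 200 | 200 | 100% |

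**A against B.** DMF intake is identical, but the duration doubles because a later zero-dose record was entered. The category moves from at most 24 weeks (168 days) to more than 24 and up to 48 weeks.

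**C.** The end date is set to EOT on the strength of a record that begins 40 days after EOT. In 5.3.3.2 that record contributes 200 − 240 + 1 = −39 days, so intake is 100 − 39 = 61 days, and 61/200 = 30.5% instead of 50%. The end of each record is trimmed to EOT, but a record starting after EOT is not excluded.

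**D.** The base rule gives 230 − 1 + 1 = 230 days, 30 days beyond study treatment. No unusual record is needed.

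**General size.** In B and C the overstatement equals EOT minus the last on-study DMF dose. With EOT at Day 400 and last doses from Day 100 to Day 393, it runs from 300 days down to 7. With EOT at Day 400, a last on-study dose on Day 200 and a restart record from Day 420 closed on Day 600, the base rule gives 600 days against 200.

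**Subject-years.** Section 9.5.2.1 sums exposure over subjects without saying which of the two exposure variables is meant. If it is duration, three subjects in an arm with 100 excess days each would add 3 × 100 / 365.25 = 0.82 subject-years. If it is the variable excluding interruptions, zero-dose records add nothing. Both the three subjects and the 100 days are illustrative.

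**The case against.** A reader might infer that subjects who came off DMF are hidden, shown as fully exposed. The SAP does not support that. Only one measure is affected by a zero-dose record. The exposure variable excluding interruptions and the compliance percentage both use the dose condition; in pattern B they show 100 days and 50%.

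It can also be said that duration is meant to span gaps. Study drug has the same pair of variables (5.3.1.1), and 5.3.2 takes their difference as interruption time. A difference between duration and intake is therefore not in itself a contradiction, and a gap followed by a restart can be called an interruption. This stands for gaps inside the study treatment period. It does not rescue the rule when the subject was not on DMF at EOT, because the assumption that DMF was ongoing then is false.

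Nor does the SAP show that a stop is logged as an open zero-dose record. The log has an end date and a reason for treatment end, so a stop may simply close the last dosed record. That is pattern A, and the rule then works. The dose condition in 5.3.3.2 shows that the case was allowed for, not that it happens.

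Finally, staying on study drug after stopping DMF is listed as an important protocol deviation (PD_PP.132), so long stretches off DMF before EOT should be few. This limits patterns B and C. It does not bear on D.

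**Conclusion.** The point holds as a literal error in one descriptive variable. *Duration of DMF treatment on study* and its categories are overstated when the last record is an open zero-dose record, when DMF stopped on study and was restarted after EOT with an open record, or when a documented DMF end date falls after EOT. Subject-years are affected only if they are summed from duration.

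For zero-dose records, intake days and compliance remain correct. For records starting after EOT they are too low, because negative days enter the sum.

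Per subject, the open-record error is the time from last on-study DMF dose to EOT. The day counts above rest on assumed dates. How many subjects are affected cannot be told from the SAP; for the open-record cases it is probably few. No efficacy analysis uses these variables. This is a minor correction, worth making because it is cheap.

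**What to change.** In 5.3.3.1, derive the DMF end date only from log records with individual dose above zero and a start date on or before EOT. Take the latest end date among them, impute EOT only if such a record is open, and cap the result at EOT.

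In 5.3.3.2, exclude records that start after EOT, or set a record's day count to zero when it would be negative.

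It would help to state in 9.5.2.1 which exposure variable is summed for subject-years.

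The cost is about one sentence in each section and a filter in the exposure program. No new data are needed.

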5.3.3.2 Compliance with DMF treatment during study treatment

Compliance is assessed as the percentage of days from the date of first study drug intake until EOT with DMF intake documented in the eCRF:

$$\frac{\text{no. of days with DMF intake documented}}{(\text{date of EOT-study treatment start date}) + 1 \text{ day}} \times 100$$

Note: Compliance below 100% is not necessarily indicative of a deviation from the protocol since the protocol mandates dose interruptions for certain very specific safety scenarios as well as based on investigator's judgment.

For reporting, the calculated compliance is categorized as follows: 100%, 99% – < 100%, 80% – < 99%, 50% – < 80%, > 0% – < 50%, 0%.

The number of days with DMF intake documented is derived as follows:

On the 'Drug Log - DMF' eCRF log form, each record collects 'DMF start date', 'DMF end date', and 'Individual dose'. If, for a record, the 'Individual dose' is > 0, it is assumed that the subject took DMF for each day covered by the record. For each record, the start date is defined to be the maximum of (DMF start date associated with the record, study treatment start date), and the end date is defined to be the minimum of (DMF end date associated with the record, EOT date).

The 'Number of days with DMF intake documented' for a subject overall is derived as the sum across all DMF drug log records.

